Maurer et al. (2014) [Germany]. The purpose of this retrospective study was to investigate the diagnostic efficacy of Ga PSMA-HBED-CC -PET imaging when compared against radical prostatectomy, templated lymph node dissection, and conventional imaging (CT, MRI). The primary inclusion criterion was intermediate-to-high risk prostate cancer scheduled to undergo radical prostatectomy. The only exclusion criterion was presence, or history, of a secondary malignancy. A total of 130 patients were reviewed. A contrast enhanced diagnostic CT was performed at the same imaging session as the PET scan. A double-trained board certified radiologist-nuclear medicine physician blinded to post-operative histopathological results analyzed all the imaging data sets (Ga PSMA-PET/CT and PET/MR). Conventional imaging was read prior to the Ga PSMA-PET data. Results yielded a patient-based ROC AUC of 0.835 (95% CI 0.763 – 0.908) for Ga PSMA-PET and an AUC of 0.691 (95% CI 0.592-0.789) for conventional imaging. For Ga PSMA-PET patient-based sensitivity was 65.9 %, specificity was 98.9%, and overall accuracy of 88.5%. In contrast, conventional imaging had a patient-based sensitivity of 43.9%, specificity of 85.4%, and an overall accuracy of 72.3%. On a template-based analysis driven by lymph node dissection, the Ga PSMA-PET sensitivity was calculated as 78.2%, specificity as 99.1%, and accuracy as 95.7%. Conventional imaging resulted in a sensitivity of 29.1%, specificity of 97.2%, and accuracy of 86.1%.

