Van Leeuwen et al. (2014) [Australia]. The purpose of this prospective trial was to assess accuracy of Ga PSMA-HBED-CC -PET/CT for lymph node staging in intermediate- and high-risk prostate cancer. Criteria for selection included planned radical prostatectomy, treatment naïve, negative bone scan, no concurrent (or history of) a secondary malignancy, and at >5% risk of metastatic lymph nodes. Patients with suspected extra-nodal disease on prior contrast-enhanced CT were excluded. Ga PSMA-HBED-CC PET/CT was performed <4 weeks before the radical prostatectomy and lymph node dissection. A total of 30 men were enrolled and evaluated. A non-contrast enhanced CT was performed at the same imaging session of the Ga PSMA-HBED-CC -PET. Images were analyzed by two nuclear medicine physicians; it is not stated if the physicians were blinded to the pathologic results or if the scan interpretations were completed prior to surgery. Results yielded a patient-based specificity of 95%, sensitivity of 64%, positive predictive value of 88%, and negative predictive value of 82%. Lymph node analysis yielded specificity of 100%, sensitivity of 58%, PPV of 94% and NPV of 98%. The mean size of true-positive metastatic lymph nodes was 4.7 mm ( $\pm$  1.4mm) and false-negative size was 2.7mm ( $\pm$  1.3mm).

Eiber et al. (2015) [Germany]. The purpose of this retrospective study was to investigate the detection rate of Ga PSMA-HBED-CC PET/CT in men with

biochemical recurrence (PSA  $\geq$  0.2 ng/mL). Only men who had undergone a radical prostatectomy, had not received chemotherapy, and had a diagnostic CT done with the PSMA imaging study were included. Men undergoing antiandrogen therapy (n=70) were included. A total of 248 subjects were included in the analysis. The active comparator was the diagnostic CT done simultaneously with the PET imaging. Scans were interpreted by a board certified radiologist and a board certified nuclear medicine physician. The reviewers were not blinded. No significant detection effect was observed with antiandrogen use ( $p=0.0783$ ). PSMA was able to identify additional areas of disease involvement in 61 subjects (24.6%) whereas CT showed additional regions in 17 subjects (6.9%). A significant limitation of the study was a lack of histopathology for outcome comparisons. Sensitivity, specificity, positive and negative predictive values are not provided.

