## 5.7. **Post-Prostatectomy Procedures**

- 5.7.1. **PSMA-positive with negative pathology.** Subjects with  $^{68}\text{Ga}$  PSMA-HBED-CC positive nodes without positive nodes on pathology, may be rescanned with CT (or MRI) to determine if the suspicious node was thought to be removed. Additionally, clinicians will have the option to order a 2nd  $^{68}\text{Ga}$  PSMA-HBED-CC PET/CT as described in Section 6.4.4.
- 5.7.2. **PSMA-positive osseous or metastatic lesions.**  $^{68}\text{Ga}$  PSMA-HBED-CC positive osseous or distant metastatic lesions will be followed by other imaging (bone scan, NaF PET, CT or MRI) at the treating physician's discretion and local standard of care.
- 5.7.3. **Biopsy.** Biopsies to determine metastases or provide information for re-staging should be performed at treating physician's discretion and per local

standard of care.

- 5.7.4. **CT or MRI.** Subjects should undergo routine standard of care imaging.
- 5.7.5. Positive disease identified by either Ga PSMA-HBED-CC PET/CT or follow-up conventional imaging will trigger locally performed anatomic measurement of lesion size(s) on both the baseline CT or MRI, and the follow-up CT or MRI of suspected site of disease.

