## 12.2. Reference standard definition:

12.2.1. Histopathology/Biopsy will be the primary determinate of tissue positivity and negativity for prostate cancer disease. Pathology date, organ, and location as well as any notes related to the pathology will be obtained from the subject chart. The anatomical region/sub-region the pathology occurred in will be assigned by the investigator team:

Ga-PSMA-HBED-CC positive findings are aimed to be confirmed by histopathology/biopsy if clinically feasible. Pathology performed 60 days before or after the Ga-PSMA-HBED-CC PET will be available for correlation.

Histopathological procedures and biopsies will be performed as clinically indicated and as per institutional protocol.

12.2.1.1. Lymph Nodes, Visceral Lesions, and Bone Lesions positive for disease by pathology.

- Lesions with positive pathologic confirmation will be regarded as positive for disease. The regionality of the resected tissue will be assigned into respective regions and sub-regions as described above in Table 12.2.

12.2.1.2. Lymph Nodes and Visceral Lesions negative for disease by pathology.

- Tissue removed and negative for pathology are considered negative for prostate cancer disease, unless subsequent conventional imaging or Ga-PSMA-HBED-CC PET imaging demonstrates that targeted tissue were not resected. In this case:

- i. Subjects can be rescanned with dedicated CT, MRI, or Ga-PSMA-HBED-CC PET/CT to determine if the suspicious Ga-PSMA-HBED-CC tissue was removed. If the tissue is confirmed as removed, this is considered negative for disease.

ii. If  $^{68}\text{Ga}$ -PSMA-HBED-CC PET/CT positive tissue is still present, a needle biopsy can be pursued at the discretion of the treating physician. Images of the procedure will be reviewed to determine if the correct tissue was biopsied.

- If the  $^{68}\text{Ga}$ -PSMA-HBED-CC PET/CT positive tissue was biopsied, a negative pathologic finding of the biopsied tissue is considered negative for disease.
- If the  $^{68}\text{Ga}$ -PSMA-HBED-CC PET/CT positive tissue was biopsied, a positive pathologic finding of the biopsied tissue is considered positive for disease.
- If biopsy or re-biopsy is not performed, or the wrong tissue was biopsied, change in node size as measured by conventional imaging and as defined below will be the criteria by which disease status will be defined.

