12.2.1.3. Bone lesions: Given the high rate of false negative biopsies for osseous metastases in subjects with prostate cancer, subjects with negative bone biopsies of  $^{68}\text{Ga}$ -PSMA-HBED-CC PET positive lesions will be further evaluated:

- If pathology demonstrates an alternative diagnoses that is known to be  $^{68}\text{Ga}$ -PSMA-HBED-CC positive (eg Renal Cell Carcinoma metastases, Paget's disease), then this will be considered negative for disease.
- If pathology is indeterminate, then follow-up imaging as described below will be performed as per clinical standards at the site.

12.2.1.4. Although not routinely performed during standard practice, immunohistochemical staining for PSMA of tumor specimens (primary and lymph node metastases) may be performed, although not required.

12.2.1.5. All regions not sampled for biopsy/histopathology will be designated as indeterminate for disease by pathology. Conventional imaging follow-up may be used in these cases to determine tissue status.

12.2.2. Follow-up Imaging will be used as a secondary assessment for prostate cancer in the event pathology information is not available:

All subjects will be tracked for follow-up conventional imaging between 3-12 months post  $^{68}\text{Ga}$ -PSMA-HBED-CC (dedicated CT, MRI and/or bone scan) as per site standard of care. If no follow-up imaging has been performed within the 9 months following the  $^{68}\text{Ga}$ -PSMA-HBED-CC scan, then the research study will pay for an additional follow-up CT scan to be performed in the 9-12

month window post-Ga-PSMA-HBED-CC scan. Follow up imaging will only be performed on subjects that have positive Ga-PSMA-HBED-CC findings because conventional imaging assessment for disease is primarily targeting suspicious lesions identified by Ga-PSMA-HBED-CC PET/CT. Interpretation of follow-up imaging will be performed by local read. Preferably, the follow-up conventional imaging should be the same modality/modalities as the initial staging work-up to allow for reproducible and accurate comparisons. Conventional imaging standards as described below will be used to determine tissue positive for prostate cancer disease. Conventional imaging will not be used to determine negative prostate cancer disease regions due to its inherently low negative predictive value.

Tissue positive for prostate cancer disease based on follow-up imaging:

12.2.2.1. Lymph nodes will be assessed by change in size.

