#### 13.2.3. False positive patient:

13.2.3.1. **Ga PSMA-HBED-CC PET/CT positive for regional nodes**

**by internal blind reader**, pathology at prostatectomy is negative, and imaging after prostatectomy demonstrates that node is no longer present as defined in Section 12.2.1.2.

13.2.3.2.  **$^{68}\text{Ga}$  PSMA-HBED-CC PET/CT positive for regional node by internal blind reader**, but pathology at prostatectomy is positive for node but in a different nodal region than the node seen on PSMA PET.

13.2.4. False negative patient:

13.2.4.1.  **$^{68}\text{Ga}$  PSMA-HBED-CC PET/CT negative for regional nodes by internal blind reader**, but pathology at prostatectomy is positive for regional nodes.

13.2.5. Non-evaluable patient:

13.2.5.1. Any subject that does not have sufficient data to meet the criteria for definition of true positive patient, true negative patient, false positive patient, or false negative will be classified as non-evaluable.

13.2.5.2. Patients with extrapelvic nodal metastases will not be included in this analysis for the primary endpoint if patients do not undergo prostatectomy.

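### The primary false-positive rule lets post-operative CT or MRI show that a PET-positive node was removed without requiring that CT or MRI could see it beforehand, so a retained metastasis can be scored as a PET false positive

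*Combined protocol and SAP*

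**What the plan says.** Section 13.2.3.1 makes a man a false positive for the primary endpoint when the blinded read is positive for regional nodes, pathology is negative, and "imaging after prostatectomy demonstrates that node is no longer present", with a reference to 12.2.1.2 for the definition.

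Section 12.2.1.2 treats pathology-negative tissue as negative for disease unless later imaging shows that the target was not resected. Its item i gives the means of checking: "Subjects can be rescanned with dedicated CT, MRI, or" repeat PSMA PET/CT. Any one of the three is enough, and tissue confirmed as removed is negative. Section 5.7.1 describes the same step more loosely: such men "may be rescanned with CT (or MRI) to determine if the suspicious node was thought to be removed". Sections 5.7.1 and 6.4.4 make the second PSMA PET/CT optional.

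Elsewhere the plan is cautious about conventional imaging. Section 12.2.2 says: "Conventional imaging will not be used to determine negative prostate cancer disease regions due to its inherently low negative predictive value". Section 12.2.1.5 says: "All regions not sampled for biopsy/histopathology will be designated as indeterminate for disease by pathology". The background (2.3) reports, for the template analysis of the 130-patient retrospective series, "Conventional imaging resulted in a sensitivity of 29.1" per cent, and for the 30-man prospective trial, "The mean size of true-positive metastatic lymph nodes was 4.7 mm".

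**The concern.** The rescan is there to separate two kinds of men with positive PET and negative pathology: those whose benign node was removed, and those whose metastatic node is still in place. CT or MRI can do this if it showed the node before surgery. If only PET showed it, CT or MRI looks the same whether the node was taken or left.

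No section makes pre-operative visibility a condition, and 13.2.3.1 does not ask whether the PET-positive sub-region was sampled. An unsampled site is foreseeable. PET is read in seven pelvic subgroups, one of them a residual category (5.5.1, Table 12-2), while the dissection examples in 5.6.3 are two or six regions with no residual one.

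With CT or MRI as the check, the error runs one way. The route back to true positive, 13.2.1.2, first needs imaging that shows the node was not removed, and CT or MRI is unlikely to show that for a node it never displayed. The misscored man leaves the true positives and joins the false positives. The affected measures are primary, and 13.1 says the pilot will inform a larger study.

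**Working it through.** The plan attaches no figure to this rule. Its one sample-size table (13.1) reproduces, for example 1.96 × √(0.80 × 0.20 / 30) = 14.3%, but does not bear on the point.

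**1. How often might CT or MRI fail to show a metastatic node?** From the 130-patient series in 2.3, conventional-imaging sensitivity is 43.9% per patient and 29.1% per template. The only whole-number split that fits the patient-level figures for both modalities is 41 node-positive and 89 node-negative men:

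- Conventional imaging: 18/41 = 43.9%, 76/89 = 85.4%, accuracy 94/130 = 72.3%.
- PSMA PET: 27/41 = 65.9%, 88/89 = 98.9%, accuracy 115/130 = 88.5%.

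The miss rate is 1 − 0.439 = 56.1% per patient and 1 − 0.291 = 70.9% per template. These serve only as a proxy for non-visualisation.

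**2. How many men might be affected?** Scale that series to 30 men. Expected PET-positive, node-positive men = 30 × (41/130) × 0.659 = 6.2. Let m be the share whose metastasis is left behind. The documents give no value, so a range is assumed. Expected misscored men = 6.2 × m × miss rate:

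| m (assumed) | miss rate 56.1% | miss rate 70.9% |
|---|---|---|
| 5% | 0.17 | 0.22 |
| 10% | 0.35 | 0.44 |
| 20% | 0.70 | 0.88 |
| 30% | 1.05 | 1.33 |

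**3. What does one such man do?** The cited 30-man trial reports sensitivity 64%, specificity 95%, PPV 88% and NPV 82%. TP 7, FN 4, FP 1, TN 18 reproduces all four: 7/11, 18/19, 7/8 and 18/22. Suppose one of the seven true positives is a PET-only node left behind. Sensitivity here is TP/(TP+FN); the formula printed in 13.1 has false positives in its denominator, which is a separate matter.

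| That man is scored as | TP | FN | FP | TN | Sensitivity | Specificity | PPV |
|---|---|---|---|---|---|---|---|
| True positive | 7 | 4 | 1 | 18 | 7/11 = 63.6% | 18/19 = 94.7% | 7/8 = 87.5% |
| False positive | 6 | 4 | 2 | 18 | 6/10 = 60.0% | 18/20 = 90.0% | 6/8 = 75.0% |
| Non-evaluable | 6 | 4 | 1 | 18 | 6/10 = 60.0% | 18/19 = 94.7% | 6/7 = 85.7% |

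NPV is 18/22 = 81.8% in every row. Moving the man from false positive to non-evaluable repairs specificity and most of PPV, and leaves sensitivity at 6/10.

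**The case against.** The strongest reply is that the rule is already strict. Imaging must demonstrate that the node is gone and confirm that the tissue was removed, and a scan blank both before and after surgery does neither. On that reading the man lacks sufficient data and is non-evaluable under 13.2.5.1. Likewise, 12.2.1.2 concerns tissue that was removed, and 12.2.1.5 already makes unsampled regions indeterminate. This reading is possible, but the text does not secure it. No section states the visibility condition, the patient-level rule does not repeat 12.2.1.5, and the default in 12.2.1.2 is negative unless imaging shows the target was missed.

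Other parts of the reply stand, and they limit what a reader might infer:

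- **That CT or MRI would miscall 56% to 71% of retained nodes.** The cited sensitivities are for calling nodal metastasis across all node-positive patients or templates, including those PET missed. They are not for seeing a node at a known location, and 6.4.2 tells follow-up readers where the PET-positive lesions are.
- **That the plan contradicts its own bar in 12.2.2.** That bar is written for cases without pathology. In 13.2.3.1 the negative call comes from pathology, and imaging addresses removal only. The bar does bear on a sub-region that was never sampled.
- **That many men will be misscored.** The surgeon is told the PET location and asked to try to capture the node (5.6.2), and repeat PSMA PET/CT is available, though optional.
- **That a stricter rule would correct the sensitivity estimate.** The table above shows that it does not.

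**Conclusion.** The gap is real. As written, the rule allows a retained, PET-only metastasis to be scored as a PET false positive, which lowers specificity and PPV and loses a true positive. It is a gap in a scoring definition, not a demonstrated bias.

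The number of men is unknown. It is below one in 30 if up to 20% of PET-positive metastases are left behind and the proxy miss rates hold, and slightly above one at 30%. One man is enough to matter: 4.7 points of specificity and 12.5 points of PPV in the worked example. The example assumes that the pilot resembles the cited 30-man trial and that exactly one man is affected. The documents do not support a claim that the rule will materially distort the pilot's sensitivity target.

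**What to change.** In 13.2.3.1 and 12.2.1.2.i, state what counts as proof of removal for scoring:

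- Post-operative CT or MRI counts only if the node was identifiable on pre-operative CT or MRI (including the CT part of the PET/CT) and is absent afterwards.
- A repeat PSMA PET/CT that no longer shows the node also counts, where one was done.
- Otherwise the man is non-evaluable under 13.2.5.1, in line with 12.2.1.5 for unsampled regions.

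Report the number of such men, and give sensitivity, specificity and PPV with all of them scored as false positives and again with all scored as true positives, beside the main result.

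A negative specimen packet from the PET-positive area should not be accepted as proof of removal by itself. A packet can hold other nodes while the suspicious one stays behind, 5.6.3 allows packets that are only left and right, and the criterion would create false positives without the imaging that 13.2.3.1 now requires.

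The cost is wording, plus a recorded judgement of pre-operative visibility from images the study already holds (5.7.5, 6.1). No scan is added and patient care does not change. The downside is that a few men may become non-evaluable, and excluding them alone would push specificity and PPV upward. That is why the results scored both ways are needed.

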## 1. OBJECTIVES

### 1.1. Primary objective

- 1.1.1. Determine sensitivity, specificity, positive, and negative predictive value of  $^{68}\text{Ga}$  PSMA-HBED-CC PET for detection of regional pelvic nodal metastases compared to pathology at radical prostatectomy (per patient, using nodal regional correlation).

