## 13. STATISTICAL CONSIDERATIONS

### 13.1. Statistical Justification

This study is a pilot study to determine target sensitivity for Ga PSMA-HBED-CC for the detection of prostate cancer in the pre-prostatectomy population. Based upon literature, we anticipate sensitivities of > 80% in this patient population, but there are uncertainties, particularly related to the proposed reference standard. We plan to use the results of this pilot study, potentially combined with reported results from other sites across the US performing similar studies (same patient population, same methods, same reference standard definitions...) to determine most-appropriate primary endpoint sensitivities for a larger University of Iowa study to follow this one, so as to appropriately statistically power the larger study.

The primary objective of this pilot study is to obtain preliminary information on the sensitivity of physician reads for Ga-68 PSMA pre-prostatectomy; physicians' ability to correctly identify prostate cancer and metastases via Ga-68 PSMA relative to our pathology/conventional imaging reference standard. Due to the lack of clinical experience with this radiopharmaceutical, this pilot study is meant to gain meaningful information of the sensitivity of this agent in this patient population to generate hypotheses for further trials.

To evaluate sensitivity, patients must undergo both Ga-68 PSMA imaging and evaluation for prostate cancer by pathology, follow-up conventional imaging, or both. Sensitivity is defined as:

$$Sensitivity = \frac{\text{number of true positives (TP)}}{\text{number of true positives (TP)} + \text{number of false positives (FP)}}$$

The table below provides 95% confidence interval half-widths for a range of sensitivity values based on a planned sample size of 30 patients using a normal approximation.

Sensitivity	Half-Width
70%	16.4%
75%	15.5%
80%	14.3%
85%	12.8%
90%	10.7%

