#### 13.2.1. True positive patient:

13.2.1.1. **Ga PSMA-HBED-CC PET/CT positive for a regional node by internal blind reader:** pathology at prostatectomy is positive for a regional node that correlates in location to the PET images (location on pathology is determined by the urologist at the time of the surgery). Only one node needs to correspond between imaging and pathology for a patient to be considered a true positive.

13.2.1.2. **Ga PSMA-HBED-CC PET/CT positive for regional nodes by internal blind reader,** pathology negative for regional nodes, imaging after prostatectomy demonstrates the same node was not removed at surgery, and follow-up biopsy or imaging demonstrates presence of nodal disease as defined in Section 12.2.1.2 .

13.2.1.3. **Conventional imaging criteria for positive node on follow-up imaging:** imaging within 3-12 months, the node decreases by more than 30% (for patients undergoing systemic treatment or focal therapy at this site) or increase by more than 20% in short axis diameter in the absence of treatment (with a minimum of 3 mm in change in size) as defined in Section 12.2.2.1 .

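### Section 13.2.3.2 counts a PET-positive patient with proven nodal disease in another region as a false positive, which moves him out of the sensitivity denominator and into the specificity denominator

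*Combined protocol and SAP*

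**What the plan says.** The primary objective (1.1.1) is to be assessed "per patient, using nodal regional correlation". Section 13.2 then sorts each patient into one class:

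- **True positive.** 13.2.1.1 needs a location match, and "Only one node needs to correspond between imaging and pathology for a patient to be considered a true positive". 13.2.1.2 covers a PET-positive patient with "pathology negative for regional nodes, imaging after prostatectomy demonstrates the same node was not removed at surgery", followed by proof of disease. 13.2.1.3 covers nodes that meet the follow-up criteria of 12.2.2.1; it states no condition on surgical pathology.
- **False positive.** 13.2.3.1 covers negative pathology and also requires that "imaging after prostatectomy demonstrates that node is no longer present". 13.2.3.2 covers a positive PET when "pathology at prostatectomy is positive for node but in a different nodal region than the node seen on PSMA PET". It asks for no further evidence.
- **False negative.** 13.2.4.1 requires a negative PET, "but pathology at prostatectomy is positive for regional nodes".

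No order of precedence among these rules is stated. On untested tissue, 12.2.1.5 says: "All regions not sampled for biopsy/histopathology will be designated as indeterminate for disease by pathology". Section 13.1 says the pilot will be used "to determine most-appropriate primary endpoint sensitivities for a larger University of Iowa study to follow this one", possibly together with results from similar sites.

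**The concern.** Sensitivity is a proportion among patients with the disease, and specificity a proportion among patients without it. A mismatch patient has positive regional nodes on histology, so by the reference standard he has nodal disease. Refusing him true-positive credit is one decision; placing him among the disease-free is another, and 13.2.3.2 does both. He is never counted as a missed case.

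The rule can also call a PET finding false when nothing has refuted it. If the PET-positive region was not sampled, 12.2.1.5 leaves it indeterminate, yet 13.2.3.2 still gives a false positive. 13.2.3.1 is stricter, because it wants imaging evidence that the node has gone.

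At stake is the meaning of the pilot's main output. Those who plan the larger study need to know whether the reported sensitivity is location-matched or location-free.

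**Working it through.** **1. The plan's own figure.** Section 13.1 tabulates 95% half-widths for n = 30. The formula 1.96 × √(p(1−p)/30) gives 16.4, 15.5, 14.3, 12.8 and 10.7 points at p = 70, 75, 80, 85 and 90%. All five agree with the plan, and none depends on the rule discussed here.

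**2. Which class fits.** Take a patient who is PET-positive, has positive nodes at prostatectomy and has no location match.

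- 13.2.1.1 fails: no match.
- 13.2.1.2, read literally, fails: his surgical pathology is not negative.
- 13.2.1.3 is possible, but only if a PET-positive node remains and meets 12.2.2.1 on follow-up.
- 13.2.2.1 and 13.2.4.1 fail: PET is positive.
- 13.2.3.1 fails: pathology is positive.
- 13.2.3.2 applies.

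Without qualifying follow-up, false positive is the only class left.

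**3. Formulas.** Use sensitivity = TP/(TP+FN) and specificity = TN/(TN+FP). Section 13.1 prints TP/(TP+FP) as sensitivity; that is the formula for positive predictive value (PPV), a separate error, and it is not used here. Let TP include m mismatches before they are reclassified.

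- Plan: sensitivity (TP−m)/(TP+FN−m); specificity TN/(TN+FP+m).
- Mismatch as a miss: sensitivity (TP−m)/(TP+FN); specificity TN/(TN+FP).
- Location-free: sensitivity TP/(TP+FN); specificity TN/(TN+FP).

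For m > 0, the plan's specificity is lower whenever TN > 0. The plan's sensitivity exceeds the miss value if at least one matched true positive remains, and lies below the location-free value if FN > 0.

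**4. Illustration.** Section 2.3 gives the per-patient results of the 30-man prospective study as sensitivity 64%, specificity 95%, PPV 88% and negative predictive value (NPV) 82%. The only 2×2 table of 30 that rounds to all four is TP 7, FN 4, FP 1, TN 18. The values of m are assumed.

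| m | Sensitivity, plan | Sensitivity, miss | Sensitivity, location-free | Specificity, plan | Specificity, other two |
|---|---|---|---|---|---|
| 0 | 7/11 = 63.6% | 7/11 = 63.6% | 7/11 = 63.6% | 18/19 = 94.7% | 18/19 = 94.7% |
| 1 | 6/10 = 60.0% | 6/11 = 54.5% | 7/11 = 63.6% | 18/20 = 90.0% | 18/19 = 94.7% |
| 2 | 5/9 = 55.6% | 5/11 = 45.5% | 7/11 = 63.6% | 18/21 = 85.7% | 18/19 = 94.7% |

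At m = 1, PPV under the plan is 6/8 = 75.0%, the same as when the mismatch is kept as an unconfirmed PET-positive. NPV stays at 18/22 = 81.8%, because the patient is PET-positive.

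**5. A larger table.** The 130-patient retrospective study in 2.3 (sensitivity 65.9%, specificity 98.9%, accuracy 88.5%) fits only TP 27, FN 14, FP 1, TN 88. One assumed mismatch gives sensitivity 26/40 = 65.0% under the plan, 26/41 = 63.4% as a miss and 27/41 = 65.9% location-free. Specificity is 88/90 = 97.8% against 88/89 = 98.9%.

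**6. Against sampling error.** In the 30-man table the 95% half-width is 1.96 × √(0.636 × 0.364/11) = 28.4 points for sensitivity and 1.96 × √(0.947 × 0.053/19) = 10.0 points for specificity. One mismatch moves specificity by 4.7 points. It puts the plan's sensitivity 5.5 points above the miss value and 3.6 points below the location-free value.

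**The case against.** The location requirement is deliberate. Objective 1.1.1 states it, and the secondary endpoints repeat the different-region rule in 13.3.3. That stands as a reason to withhold true-positive credit. It gives no reason to count a node-positive man among the disease-free.

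The effect is conditional and small, and the endpoint is descriptive. That also stands. One matching node is enough for a true positive, the surgeon is told where the PET-positive nodes are (5.6.2), and template-based specificity in the 130-patient study was 99.1%, so mismatches are probably uncommon. The cited tables may already be location-matched.

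The planned data already allow a location-free table, since pathology is reported per patient and by region (5.6.4). True, but the plan does not say it will be reported.

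Stronger readings are tempting but unsupported:

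- A reader might infer that such a patient can only ever be a false positive. 13.2.1.3 may still reach him. It refers to 12.2.2.1, which includes a PSA-based route as well as size criteria. The tissue-level wording of 12.2.1.2 also leaves room for a wider reading of 13.2.1.2.
- A reader might infer that the plan inflates sensitivity. The direction depends on the comparator.
- A reader might infer that 12.1.1.1 flatly contradicts 13.2, because it says pelvic sub-region data do not directly serve the primary endpoint. The word directly, and the statement in section 12 that region results are derived from sub-region data, make this a matter of wording.

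**Conclusion.** The rule is wrong as written, with modest expected size. Whenever a mismatch occurs and no other true-positive route applies, a reference-positive patient leaves the sensitivity denominator and enters the specificity denominator. This follows from 13.2.1 to 13.2.4 and the standard formulas, without any numerical assumption. Specificity is then understated (if TN > 0). Sensitivity lies between the two usual quantities when FN > 0 and a matched true positive remains, and so equals neither.

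The size is not known. The figures above rest on an assumed mismatch count and on tables recovered from rounded percentages. It would go too far to conclude that the pilot's results will be materially distorted: one case is small against the sampling error, and the effect is zero if none occurs. A confidence interval does not correct a misclassification, however, so the rule should be settled before patients are classified.

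**What to change.** Amend 13.2 as follows.

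1. State that all routes in 13.2.1 are checked first.
2. Make 13.2.3.2 its own category: reference-positive, PET-positive, no location match. Keep these patients in the sensitivity denominator and out of the specificity denominator.
3. Report two labelled sensitivities: location-matched, with these patients uncredited, and location-free per patient. In PPV count them as unconfirmed (denominator only); NPV is unchanged.
4. Report their number and, where the data allow, how many had the PET-positive region unsampled.
5. Keep the tabulation under the present 13.2.3.2 for pooling, which 13.1 limits to sites with the same reference standard definitions.
6. Reconcile the wording of 12.1.1.1 with the location matching in 13.2. State that matching uses the surgical packets of 5.6.3, and report the packet scheme for each mismatch. PET uptake in the left obturator region with disease in the left external iliac region matches under a left/right division but not under six groups. One imposed mapping would be a debatable trade-off, because to cover every patient it might have to be as coarse as left/right.

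The cost is an amendment to a primary-endpoint category and some analysis work. The two sensitivities can be tabulated from planned data. The detail in item 4 may be incomplete where pathology arrives only as left and right packets. The location-matched sensitivity may come out a few points lower than under the present rule (5.5 and 1.6 points in the two illustrations), and two sensitivities must be explained.
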